1.2. Schema

Figure 1: Schema for Participants in Need of Retreatment at Study Entry

EoP=end of study/early discontinuation visit for antecedent studies ARGX-113-2001 or ARGX-113-1705; EoS=end of study; gMG=generalized myasthenia gravis; IMP=investigational medicinal product; IP_nVm=intertreatment period (period number) visit (visit number); PH20=recombinant human hyaluronidase PH20 (rHuPH20); q7d=every 7 days; SC=subcutaneous(ly); SoA=schedule of activities; TP=treatment period; TP_nVm=treatment period (period number) visit (visit number)

[figure not shown]
^a Participants will receive efgartigimod PH20 SC 1000 mg q7d for a total of 4 injections in a TP. A new TP can be started if the participant is in need of retreatment as determined by the investigator, however during the first year, at least 28 days must have elapsed since the last dose of efgartigimod. During the second year onward, it is recommended to have at least 28 days between TPs. However, a subsequent treatment period can be administered earlier based on clinical evaluation at the discretion of the investigator, with a minimum interval of 7 days after the last IMP administration. In case of retreatment, there must be at least 4 weeks left in the study for the participant, so that a full TP and the EoS visit can be performed.

^b For the visit schedule, see the SoA (Section 1.3).

^c Participants will remain in the study for at least 1 year, until efgartigimod PH20 SC becomes commercially available or available through another continued access program for gMG, or until 31 Dec 2024, whichever comes first.

^d Dose reduction or changes to the dose are allowed as described in Section 6.8.2. Concomitant gMG treatment can be tapered completely.

Figure 2: Schema for Participants Not in Need of Retreatment at Study Entry

EoP=end of study/early discontinuation visit for antecedent studies ARGX-113-2001 or ARGX-113-1705; EoS=end of study; gMG=generalized myasthenia gravis; IMP=investigational medicinal product; IP_nVm=intertreatment period (period number) visit (visit number); PH20=recombinant human hyaluronidase PH20 (rHuPH20); q7d=every 7 days; SoA=schedule of activities; TP=treatment period; TP_nVm=treatment period (period number) visit (visit number)

^a During the intertreatment period, visits will occur every 21 days. TP₁V1 will occur when a participant is eligible for retreatment.

^b Participants will receive efgartigimod PH20 SC 1000 mg q7d for a total of 4 injections in a TP. A new TP can be started if the participant is in need of retreatment as determined by the investigator, however during the first year, at least 28 days must have elapsed since the last dose of efgartigimod. During the second year onward, it is recommended to have at least 28 days between TPs. However, a subsequent treatment period can be administered earlier based on clinical evaluation at the discretion of the investigator, with a minimum interval of 7 days after the last IMP administration. In case of retreatment, there must be at least 4 weeks left in the study for the participant, so that a full TP and the EoS visit can be performed.

^c For the visit schedule, see the SoA (Section 1.3).

^d Participants will remain in the study for at least 1 year, until efgartigimod PH20 SC becomes commercially available or available through another continued access program for gMG, or until 31 Dec 2024, whichever comes first.

^e Dose reduction or changes to the dose are allowed as described in Section 6.8.2. Concomitant gMG treatment can be tapered completely.

1.3. Schedule of Activities

Table 1: Schedule of Activities for Year 1

Visit Type	Treatment Period						Intertreatment Period		ET/SFU ^{b,e}	UNS ^f
	TP _n V1 ^{a,b}	PK1 ^{b,c}	TP _n V2	TP _n V3	TP _n V4	PK2 ^{b,c}	IP _n V1 ^b	IP ₀ V1 ^{a,b} / IP _n Vm ^d		
Study Day (Visit Window)	A	A+2 (±1)	A+7 (±2)	A+14 (±2)	A+21 (±2)	A+23 (±1)	A+28 (±2)	Y+21 (+7)	NA	NA
Informed consent	X ^g							X ^g		
Inclusion/exclusion criteria	X ^g							X ^g		
Demographic characteristics	X ^g							X ^g		
Weight	X ^g							X ^g	X	X
MG-ADL ^h	X		X ⁱ	X ⁱ	X ⁱ		X	X ⁱ	X	X
MG-QoL15r	X		X ⁱ	X ⁱ	X ⁱ		X	X ⁱ	X	X
EQ-5D-5L	X						X	X ⁱ	X	X
SIB risk monitoring ^m	X		X ⁱ	X ⁱ	X ⁱ		X	X ⁱ	X	X
Single 12-lead ECG	X						X	X	X	X
Physical examination	X						X	X	X	X

Visit Type	Treatment Period						Intertreatment Period		ET/SFU ^{b,e}	UNS ^f
	TP _n V1 ^{a,b}	PK1 ^{b,c}	TP _n V2	TP _n V3	TP _n V4	PK2 ^{b,c}	IP _n V1 ^b	IP ₀ V1 ^{a,b} / IP _n Vm ^d		
Study Day (Visit Window)	A	A+2 (±1)	A+7 (±2)	A+14 (±2)	A+21 (±2)	A+23 (±1)	A+28 (±2)	Y+21 (+7)	NA	NA
Vital signs	X						X	X	X	X
Safety laboratory tests ^h	X						X	X	X	X
Vaccination antibody titers and PBMCs ^o	(X)		(X)	(X)	(X)		(X)	(X)	(X)	X
Immunogenicity ^p	X						X	X	X	X
Pharmacodynamics ^q	X						X	X	X	X
Pharmacokinetics	X ^r	X				X	X		X	X
SARS-CoV-2 test ^s										X
Urinalysis	X						X	X	X	X
Urine pregnancy test ^t	X						X	X	X	X
Efgartigimod PH20 SC administration training ^u	X		(X)	(X)	(X)		X	(X)		X
Efgartigimod PH20 SC administration ^v	X		X ⁱ	X ⁱ	X ⁱ					

Visit Type	Treatment Period						Intertreatment Period		ET/SFU ^{b,e}	UNS ^f
	TP _n V1 ^{a,b}	PK1 ^{b,c}	TP _n V2	TP _n V3	TP _n V4	PK2 ^{b,c}	IP _n V1 ^b	IP ₀ V1 ^{a,b} / IP _n Vm ^d		
Study Day (Visit Window)	A	A+2 (±1)	A+7 (±2)	A+14 (±2)	A+21 (±2)	A+23 (±1)	A+28 (±2)	Y+21 (+7)	NA	NA
Administration compliance monitoring ^w	Continuous monitoring ⁱ									
Assessment of injection site ^x	Continuous monitoring ⁱ									
Hospitalization monitoring ^y	Continuous monitoring ⁱ									
Adverse events ^y	Continuous monitoring ⁱ									
Prior/concomitant therapy and procedures ^y	Continuous monitoring ⁱ									

A=day 1 of a TP; AChR-Ab=anti-acetylcholine receptor antibody; ADA=antidrug antibodies; AE=adverse event; eCRF=electronic case report form; ECG=electrocardiogram; ET=end of treatment; FSH=follicle-stimulating hormone; ICF=informed consent form; IgG =immunoglobulin G; IMP=investigational medicinal product; IP=intertreatment period; IP_nVm=IP (period number) visit (visit number); [REDACTED]; MG-ADL=Myasthenia Gravis Activities of Daily Living; MG-QoL15r=Myasthenia Gravis Quality of Life 15 item scale revised; NA=not applicable; NAb=neutralizing antibody; PBMC=peripheral blood mononuclear cell; PD=pharmacodynamics; PH20=recombinant human hyaluronidase PH20 (rHuPH20); PHQ-9=9-item Patient Health Questionnaire; PK=pharmacokinetics; PK1 and PK2=additional pharmacokinetic sample visits for subset of participants; SC=subcutaneous(ly); SFU=safety follow-up; SIB=Suicidal Ideation and Behavior; SoA=schedule of activities; TP=treatment period; TP_nV_m=TP (period number) visit (visit number); [REDACTED]; UNS=unscheduled; (X)=optional activity, only done under specified conditions; Y=previous IP visit

Note: All activities will be performed predose on dosing days, unless otherwise indicated.

^a The transition from the antecedent studies ARGX-113-1705 or ARGX-113-2001, to study ARGX-113-2002, can either be IP₀V1 or TP₁V1, depending on the need for retreatment. The first visit of study ARGX-113-2002 will always coincide with the last visit from studies ARGX-113-2001 or ARGX-113-1705. Overlapping activities performed for the last visit of these antecedent studies will not be repeated for the first visit of ARGX-113-2002.

^b This visit must always be performed at the site. All other visits can be performed by phone if IMP administration occurs at home.

^c These are optional visits to collect additional PK samples from consenting participants. These additional visits can only be performed when all of the injections of that treatment period are given at the site. Sampling will only be performed during a participant's first and/or second treatment periods that start during the first year.

^d These IP visits will occur every 21 days. The visit denominator ("m") will start at 2 for each IP after a TP. At each of these IP visits performed on-site, an evaluation of the need for retreatment will be done prior to performing any activities so that only activities listed for IP_nVm or TP_nV1 are performed, respectively. The first visit of an IP after a TP, called IP_nV1, must occur on-site. The second IP visit (IP_nV2) will also be on-site. Subsequent visits may alternate between telephone and on-site visits. During an IP, consecutive telephone visits are not allowed, except in exceptional circumstances caused by the COVID-19 pandemic and after approval by the sponsor and/or the CRO.

^e For participants who discontinue early from the study, the activities will depend on the visit at which the participant had to discontinue. Participants who discontinue early from the study at either a TP visit or an IP visit should perform planned activities for the ET visit if 49 (± 2 days) days has not elapsed since the last dose of efgartigimod. These participants will not receive any further administration of efgartigimod PH20 SC during the study and will return for the SFU visit 49 ± 2 days after the last dose administration. If 49 ± 2 days has already elapsed since the last administration of efgartigimod PH20 SC, then this visit becomes the SFU visit and the SFU visit activities must be performed. Participants who discontinue early from the study between visits should perform the SFU visit at least 49 ± 2 days after the last dose administration. If 49 ± 2 days has already elapsed since the last administration of efgartigimod, then the SFU visit will be planned as soon as possible.

^f A UNS visit can occur at the request of the participant or the investigator. During the UNS visit, activities indicated in the SoA can be performed at the discretion of the investigator, depending on the reason for the UNS visit.

^g These activities are only performed at study entry.

^h It is recommended to perform the MG-ADL scale prior to all other activities.

ⁱ When a visit is performed by phone, only these activities must be performed.

^j [REDACTED]
^k [REDACTED]
^l [REDACTED].

^m The SIB Risk Monitoring assessment is based on question 9 of the PHQ-9.

ⁿ Blood samples for clinical laboratory (hematology/clinical chemistry/coagulation panel and FSH, if applicable) safety assessments will be collected. See Section 10.2. Participants will need to be fasted for each on-site visit at which safety laboratory assessments are collected. Fasted is defined as no food or drink at least 8 hours prior to each sampling. Permitted medications that the participant normally takes can be taken as usual before a visit.

^o Additional blood samples (serum/PBMC) may need to be taken for additional/optional/future/vaccination research if the participant consents. If a participant who consents to this additional sampling receives a vaccination during the study, samples referred to in Section 8.2.9 should be taken. The closest visit that is at least 4 weeks after the vaccine was administered may be used. If this visit does not coincide with IP_nV1, then another sample will also be taken at this visit. Serum samples only need to be taken when a vaccination is planned or after a vaccination has occurred. In addition, a whole-blood sample to isolate PBMCs will be collected at study entry and then approximately every 3 months throughout the study during a scheduled on-site visit, regardless of the vaccines a participant has received.

^p Titers of ADA and the presence of NAbs against efgartigimod will be measured in serum. Blood samples for plasma titer levels of ADA and NAbs against rHuPH20 will also be taken. A titer for ADA and the presence of NAbs against PH20 must be measured at the first visit of the first TP (TP₁V1) for participants coming from study ARGX-113-1705 and for participants coming from study ARGX-113-2001 who received efgartigimod IV. If no sample is taken, the reason will be recorded. The baseline sample for ADA against rHuPH20 will not be obtained until TP₁V1.

^q The PD assessments comprises levels of total IgG, and autoantibody levels (AChR-Ab levels for AChR-Ab positive participants).

^r The PK assessments will only be taken at TP₁V1.

^s A nasopharyngeal swab will be performed to sample nasal and throat mucosal cells. Participants should only be tested for SARS-CoV-2 if they have symptoms of COVID-19 or if they were in contact with a person who tested positive for SARS-CoV-2, unless local or site regulations have more stringent testing requirements. Participants may be retested as needed. See Section 10.6.

^t Only for women of childbearing potential. See Section 8.2.7 and Section 10.5.1.

^u Participants who have not previously self-administered efgartigimod PH20 SC in study ARGX-113-2001 will be instructed on self-administration as of TP₁V1 or IP₀V1 in study ARGX-113-2002. Training can continue until the participant or caregiver is ready to administer efgartigimod PH20 SC to the satisfaction of the site staff (a minimum of 1 visit). The participant or caregiver will then perform an administration under the supervision of site staff. Therefore, a minimum of 2 visits is required for a participant or caregiver to be considered competent to administer efgartigimod PH20 SC at home. Caregivers must sign the ICF before being trained in IMP administration. (X) indicates that this activity is optional and can only be performed on-site. At every on-site visit, the study staff must review the administration log and patient diary with the participant.

^v The first dose administration of all TPs must be performed on-site, even if the dose is self-administered. Subsequent administrations in any TP may be performed at home, if the participant or caregiver has been trained and is competent to perform IMP administration. Participants or caregivers who were competent to administer efgartigimod PH20 SC in study ARGX-113-2001 may continue administration during study ARGX-113-2002 and may perform all but the first administration of a TP at home. For participants who have not previously received efgartigimod PH20 SC, self-administration or caregiver-supported self-administration can begin during the first TP if the participant or caregiver is trained and capable, but all these administrations must still be performed on-site under supervision by the site staff. During subsequent TPs, administration for visits 2, 3, and 4 may be performed at home. When IMP administration is performed at home, the associated visit will be performed by phone.

^w When administration is performed at home, participant compliance with the efgartigimod PH20 SC dosing and administration schedule will be assessed by direct questioning at each visit. Any deviations from the planned dosage must be recorded. See Section 6.4.

^x When a participant is not on-site, they must record any observed injection site reaction in the patient diary. The investigator will evaluate all reported injection site reactions and decide whether the site reaction is classified and reported as an AE.

^y Adverse events (including ongoing AEs from the antecedent studies), use of concomitant therapies, use of rescue therapy, medical procedures performed on the participants, and hospitalizations will be collected from ICF signature until the last study-related activity. All available vaccination history for participants rolling over from ARGX-113-1705 should be recorded in the eCRF. All vaccines received during the study should be recorded as concomitant medication. See Section 6.8 and Section 8.3.

Table 2: Schedule of Activities for Year 2 Onward

Visit Type	Treatment Period		Intertreatment Period ^a		ET/EoS/SFU ^{b,c,d}	UNS ^e
	TP _n V1 ^{b,c}	TP _n V2/V3/V4	IP _n V1	IP _n Vm ^{b,c}		
Study Day (Visit Window)	A	A+7/14/21 (±2)	A+28 (±2)	Y+21 (+7)	NA	NA
MG-ADL ^f	X		X	X	X	X
SIB risk monitoring ^g	X		X	X	X	X
Single 12-lead ECG	X			X ^h	X	X
Vital signs	X			X ^h	X	X
Physical examination	X			X ^h	X	X
Weight					X	X
Safety laboratory tests ⁱ	X			X ^h	X	X
Vaccination antibody titers and PBMCs ^j	(X)	(X)	(X)	(X)	(X)	X
Immunogenicity ^k	X			X ^h	X	X
SARS-CoV-2 test ^l						X
Urinalysis	X			X ^h	X	X
Urine pregnancy test ^m	X			X ^h	X	X
Efgartigimod PH20 SC administration training ⁿ	(X)	(X)	(X)	(X)	(X)	X
Efgartigimod PH20 SC administration ^o	X	X				
Administration compliance monitoring ^p	Continuous monitoring					
Assessment of injection site ^q	Continuous monitoring					
Hospitalization monitoring ^r	Continuous monitoring					

Visit Type	Treatment Period		Intertreatment Period ^a		ET/EoS/SFU ^{b,c,d}	UNS ^e
	TP _n V1 ^{b,c}	TP _n V2/V3/V4	IP _n V1	IP _n Vm ^{b,c}		
Study Day (Visit Window)	A	A+7/14/21 (±2)	A+28 (±2)	Y+21 (+7)	NA	NA
Adverse events ^f	Continuous monitoring					
Prior/concomitant therapy and procedures ^g	Continuous monitoring					

A=day 1 of a TP; ADA=antidrug antibodies; AE=adverse event; eCRF=electronic case report form; ECG=electrocardiogram; EoS=end of study; ET=end of treatment; FSH=follicle-stimulating hormone; gMG=generalized myasthenia gravis; ICF=informed consent form; IMP=investigational medicinal product; IP=intertreatment period; IP_nVm=IP (period number) visit (visit number); MG-ADL=Myasthenia Gravis Activities of Daily Living; NA=not applicable; NAb=neutralizing antibody; PBMC=peripheral blood mononuclear cell; PH20=recombinant human hyaluronidase PH20 (rHuPH20); PHQ-9=9-item Patient Health Questionnaire; SC=subcutaneous(ly); SFU=safety follow-up; SIB=Suicidal Ideation and Behavior; SoA=schedule of activities; TP=treatment period; TP_nVm=TP (period number) visit (visit number); UNS=unscheduled; (X)=optional activity, only done under specified conditions; Y=previous IP period visit
Note: All activities will be performed predose on dosing days, unless otherwise indicated. If a participant enters year 2 of the study during a TP, the remaining TP visits and subsequent IPnV1 must be completed according to the year 1 SoA (refer to [Table 1](#)).

^a IPnV1 can become a TPn+1V1 if there are at least 7 days past the last IMP administration in the previous TP, and the participant is in need of retreatment. All IPnVm visits may also become a new TP, if the investigator determines there is a need for retreatment. The need for retreatment will be assessed prior to performing any activities, so that only activities listed for IPnV1/m or TPn+1V1 are performed, respectively. The visit denominator ("m") will start at 2 for each IP after a TP.

^b Participants will remain in the study for at least 1 year, until efgartigimod PH20 SC becomes commercially available or available through another continued access program for gMG, or until 31 Dec 2024, whichever comes first.

^c On-site visits are required for TPnV1, for IPnV5/10/15, etc, (ie, every 5 visits), and for ET, EoS, and SFU visits. All other visits in Table 2 can be performed by phone, including TPnV2/3/4 in case of IMP home administration.

^d For participants who discontinue early from the study, the activities will depend on the visit at which the participant had to discontinue. Participants who discontinue early from the study at either a TP visit or an IP visit should perform planned activities for the ET visit if 49 (±2 days) days has not elapsed since the last dose of efgartigimod. These participants will not receive any further administration of efgartigimod PH20 SC during the study and will return for the SFU visit 49 ±2 days after the last dose administration. If 49 ±2 days has already elapsed since the last administration of efgartigimod PH20 SC, then this visit becomes the SFU visit and the SFU visit activities must be performed. Participants who discontinue early from the study between visits should perform the SFU visit at least 49 ±2 days after the last dose administration. If 49 ±2 days has already elapsed since the last administration of efgartigimod, then the SFU visit will be planned as soon as possible.

^e A UNS visit can occur at the request of the participant or the investigator. During the UNS visit, activities indicated in the SoA can be performed at the discretion of the investigator, depending on the reason for the UNS visit.

^f It is recommended to perform the MG-ADL scale prior to all other activities.

^g The SIB Risk Monitoring assessment is based on question 9 of the PHQ-9.

^h These assessments will only be performed every 5 visits (IPnV5, IPnV10, etc).

ⁱ Blood samples for clinical laboratory (hematology/clinical chemistry/coagulation panel and FSH, if applicable) safety assessments will be collected. See Section 10.2. Participants will need to be fasted for each on-site visit at which safety laboratory assessments are collected. Fasted is defined as no food or drink at least 8 hours prior to each sampling. Permitted medications that the participant normally takes can be taken as usual before a visit.

^j Additional blood samples (serum/PBMC) may need to be taken for additional/optional/future/vaccination research if the participant consents. If a participant who consents to this additional sampling receives a vaccination during the study, samples referred to in Section 8.2.9 should be taken. The closest visit that is at least 4 weeks after the vaccine was administered may be used. If this visit does not coincide with IPnV1, then another sample will also be taken at this visit. Serum samples only need to be taken when a vaccination is planned or after a vaccination has occurred. In addition, a whole-blood sample to isolate PBMCs will be collected at study entry and then approximately every 3 months throughout the study during a scheduled on-site visit, regardless of the vaccines a participant has received.

^k Titers of ADA and the presence of NAbs against efgartigimod will be measured in serum. Blood samples for plasma titer levels of ADA and NAbs against rHuPH20 will also be taken, but these will only be analyzed if needed for safety purposes.

^l A nasopharyngeal swab will be performed to sample nasal and throat mucosal cells. Participants should only be tested for SARS-CoV-2 if they have symptoms of COVID-19 or if they were in contact with a person who tested positive for SARS-CoV-2, unless local or site regulations have more stringent testing requirements. Participants may be retested as needed. See Section 10.6.

^m This activity is only for women of childbearing potential. See Section 10.5.2.1.

ⁿ Training can continue until the participant or caregiver is ready to administer efgartigimod PH20 SC, to the satisfaction of the site staff (a minimum of 1 visit) before performing an administration under the supervision of site staff. Therefore, a minimum of 2 visits is required for a participant or caregiver to be considered competent to administer efgartigimod PH20 SC at home. Caregivers must sign the ICF before being trained in IMP administration.

^o The first dose administration of all TPs (TPnV1) must be performed on-site, even if the dose is self-administered or administered by the caregiver. Subsequent administrations in any TP (TPnV2/3/4) may be performed at home, if the participant or caregiver has been trained and is competent to perform IMP administration. When IMP administration is performed at home, the associated visit will be performed by phone.

^p When administration is performed at home, participant compliance with the efgartigimod PH20 SC dosing and administration schedule will be assessed by direct questioning at each phone visit. Any deviations from the planned dosage must be recorded. See Section 6.4.

^q When a participant is not on-site, they must record any observed injection site reaction in the patient diary. The investigator will evaluate all reported injection site reactions and decide whether the site reaction is classified and reported as an AE.

^r Adverse events (including ongoing AEs from the antecedent studies), use of concomitant therapies, use of rescue therapy, medical procedures performed on the participants, and hospitalizations will be collected from ICF signature until the last study-related activity. All vaccines received during the study should be recorded as concomitant medication. See Section 6.8 and Section 8.3.

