2.3.1. Risk Assessment

Overall, available data confirm that efgartigimod PH20 SC has been well tolerated across studies in different indications and has an acceptable safety profile.

Table 3: Potential Risks and Mitigation Strategies

Potential Clinically Significant Risk	Summary of Data/Rationale for Risk	Mitigation Strategy
Serious infection	Efgartigimod reduces IgG levels, potentially hindering immune response and increasing the risk for infection.	Exclude participants with clinically significant active infection not sufficiently resolved in the investigator's opinion (Section 5.2). Infections are considered AESIs (Section 8.3.6). Monitor for infections and temporarily interrupt IMP dosing as specified in Section 7.1.
Injection-related reactions	All therapeutic proteins can elicit immune responses, potentially resulting in hypersensitivity or allergic reactions such as rash, urticaria, angioedema, serum sickness, and anaphylactoid or anaphylactic reactions.	Monitor participants during administration and for 30 minutes thereafter for clinical signs and symptoms of injection-related reactions. Injection-related reactions are considered AEs of clinical interest (Section 8.3.7).
Injection-site reactions	Most AEs have been mild, transient injection-site reactions, including erythema, pain, bruising, pruritus, burning, tenderness, edema, induration, irritation, paresthesia, numbness, and rash. Moderate injection-site reactions occurring less frequently include burning, erythema, pain, and numbness. Mild to moderate headache is commonly reported. Localized injection-site reactions were observed in studies of efgartigimod with PH20 administered SC.	Continuously monitor participants for injection-site reactions. Injection-site reactions are considered AEs of clinical interest (Section 8.3.7).

AE=adverse event; AESI=adverse event of special interest; IgG=immunoglobulin G; IMP=investigational medicinal product; PH20=recombinant human hyaluronidase PH20 (rHuPH20); SC=subcutaneous(ly)

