6.4. Study Intervention Compliance

Participants and/or their caregivers will receive specific training for IMP administration of efgartigimod PH20 SC and guidance materials on preparation, handling, storage, and administration of the IMP (refer to Section 4.1).

When the study intervention is administered at home by the participant or caregiver, compliance with study intervention will be assessed at each visit, including phone visits. Compliance will be assessed by direct questioning during the visits and documented in the source documents and the electronic case report form (eCRF). Deviation(s) from the prescribed dosage regimen should be recorded.

A record of the quantity of efgartigimod PH20 SC dispensed to and administered by each participant must be maintained and reconciled with study intervention and compliance records. Intervention start and stop times and dates, including dates for intervention delays will also be recorded by the site staff when administration is performed at the site and by the participant when administration is performed at home. At every on-site visit, the study staff must review the administration log and patient diary with the participant.

The investigator should promote treatment compliance by stating that compliance is necessary for the participant's safety and the validity of the study. The prescribed dose, timing, and mode of administration cannot be changed. Site staff will contact the participants for the scheduled phone visits and ensure that the participant is compliant with the IMP administration schedule. All dates, start and end times of IMP administration, and any deviations from the intended regimen must be recorded in the administration log and the eCRF.

Participants will be provided with an administration log, where they will record when the IMP was administered at home and if there were any issues with the IMP administration. Participants will also receive a patient diary to record any AEs (including injection site reactions) that have occurred, what concomitant medication they have been taking, any hospitalizations, emergency room (ER) admissions, and intensive care unit (ICU) admissions. Completed diaries have to be provided to the site staff whenever the participant visits the site. Data collected from the diaries will need to be entered into the eCRF by the site staff.

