8.3.7.2. Injection-Site Reaction

An injection-site reaction is any AE developing at the injection site. Localized injection-site reactions were observed in studies of efgartigimod with PH20 administered SC. The most frequently reported injection-site reaction AEs are *Injection site erythema*, *Injection site pain*, and *Injection site swelling*.

Any injection-site reaction will be reported as an AE (Section 8.3). Certain types of local reactions could be photographed and shared with the sponsor for review and assessment.

As a routine precaution, participants will be trained or observed closely by a trained health-care professional for any potential injection-site reaction.

Refer to the current IB for more information on injection-site reactions.

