10.4.1. Definition of AE

AE Definition

- An AE is any untoward medical occurrence in a clinical study participant, temporally associated with the use of study intervention, whether or not considered related to the study intervention.
- NOTE: An AE can therefore be any unfavorable and unintended sign (including an abnormal laboratory finding), symptom, or disease (new or exacerbated) temporally associated with the use of study intervention.

Events to Be Collected as AEs

- Any abnormal laboratory test results (hematology, clinical chemistry, or urinalysis) or other safety assessments (eg, ECG, radiological scans, vital signs measurements), including those that worsen from baseline, considered clinically significant in the medical and scientific judgment of the investigator (ie, not related to progression of underlying disease).
- Exacerbation of a chronic or intermittent pre-existing condition including either an increase in frequency and/or intensity of the condition.
- New conditions detected or diagnosed after study intervention administration even though it may have been present before the start of the study.
- Signs, symptoms, or the clinical sequelae of a suspected intervention- intervention interaction.
- Signs, symptoms, or the clinical sequelae of a suspected overdose of either study intervention or a concomitant medication. Overdose per se will not be reported as an AE/SAE unless it is an intentional overdose taken with possible suicidal/self-harming intent. Such overdoses should be reported regardless of sequelae.
- “Lack of efficacy” or failure of expected pharmacological action” per se will not be reported as an AE or SAE. Such instances will be captured in the efficacy assessments. However, the signs, symptoms, and/or clinical sequelae resulting from lack of efficacy will be reported as AE or SAE if they fulfill the definition of an AE or SAE.

Events NOT to Be Collected as AEs

- Any clinically significant abnormal laboratory findings or other abnormal safety assessments which are associated with the underlying disease, unless judged by the investigator to be more severe than expected for the participant’s condition.
- The disease/disorder being studied or expected progression, signs, or symptoms of the disease/disorder being studied, unless more severe than expected for the participant’s condition.
- Medical or surgical procedure (eg, endoscopy, appendectomy): the condition that leads to the procedure is the AE.

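### Protocol 8.3.7.2 has every injection-site reaction reported as an AE, but the schedule footnotes leave AE status to the investigator; because the SAP takes these reactions only from AE records, their counts may be understated or differ by site

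*Protocol*

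**What the plan says.** Protocol 8.3.7.2 defines the event and then sets the reporting rule: "An injection-site reaction is any AE developing at the injection site" and "Any injection-site reaction will be reported as an AE (Section 8.3". Two other places agree with it. In Table 3 (Section 2.3.1) the mitigation entry reads "Injection-site reactions are considered AEs of clinical interest (Section 8.3.7", and Section 6.4 says "Participants will also receive a patient diary to record any AEs (including injection site reactions) that have occurred".

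The schedule of activities says something else. Table 1 footnote x (year 1) begins "When a participant is not on-site, they must record any observed injection site reaction in the patient diary" and goes on: "The investigator will evaluate all reported injection site reactions and decide whether the site reaction is classified and reported as an AE". Table 2 footnote q (year 2 onward) has the same text, and SAP 9.4.2 footnote q repeats it.

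On the analysis side, SAP 5.1.2 defines ISRs as those AEs that fall under the MedDRA high level term for injection site reaction, whatever the time of onset. On data flow, Section 6.4 says "Data collected from the diaries will need to be entered into the eCRF by the site staff". The SAP plans no display of site reactions that were recorded but not classified as AEs.

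**The concern.** ISRs are a named risk of this subcutaneous product, and the primary objective is long-term safety and tolerability. A site following 8.3.7.2 enters every local reaction as an AE. A site following the footnote may enter some and leave others in the diary. The same reaction could then be counted at one site and not at another, and a reader of the final tables could not tell whether the ISR incidence covers all reactions or only those an investigator chose to classify.

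The effect on the primary AE endpoint is narrower. The proportion of participants with any AE changes only for someone whose sole AE was an omitted local reaction. Event counts and rates per 100 patient-years of follow-up lose every omitted reaction.

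**Working it through.** The documents give no ISR rate and the study tests no hypothesis, so there is no figure to reproduce. The check is a comparison of texts, followed by tracing the events into the planned outputs.

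1. **Are both rules current?** Yes. Section 8.3.7.2 and the footnotes to Tables 1 and 2 all stand in the body of protocol v3.0. This is not a difference between current text and a change log.

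2. **Do they cover the same events?** They overlap. Section 8.3.7.2 covers any ISR. The footnotes certainly cover reactions that a participant writes in the diary while off-site. They already call these entries injection site reactions before the investigator acts, and what is left to decide is AE status. For those events one rule is mandatory and the other discretionary.

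3. **Is there a criterion for leaving a reaction out?** None in the footnotes, which cite neither 8.3.7.2 nor 10.4. The general definition in 10.4.1 does apply: "An AE is any untoward medical occurrence in a clinical study participant, temporally associated with the use of study intervention". Section 8.3 ties the investigator's recording duty to that definition. The list in 10.4.1 of events not to be collected does not mention local reactions, so it gives no ISR-specific ground for omission.

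4. **Does an omission reach the analysis?** Yes. If a share s of site reactions is entered as AEs, the SAP counts s times the events that 8.3.7.2 would give, a shortfall of 1 − s. It is zero only when s = 1. The documents give no value of s, overall or by site.

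5. **Which outputs are affected?**
   - The ISR row in the general AE overview tables: 14.3.1.1, 14.3.1.1B, 14.3.1.1.1 to 14.3.1.1.6, 14.3.1.17 and 14.3.1.17B, that is 1 + 1 + 6 + 1 + 1 = 10.
   - ISR-specific tables: 14.3.1.13, 14.3.1.14.1 to 14.3.1.14.6, 14.2.7.4.20 and 14.2.7.4.22, that is 1 + 6 + 2 = 9. Two more are uncertain. Table 14.2.7.4.24 depends on there being at least 5 NAb-positive participants (SAP 4.5.3). Table 14.3.1.13B is listed in SAP 8.1 but excluded by the text of 5.1.3.
   - Listing 16.2.7.8.
   - The general TEAE tables into which ISR preferred terms feed, such as 14.3.1.2, 14.3.1.3, 14.3.1.5 and 14.3.1.7.

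6. **Could the omitted reactions be recovered?** Perhaps. Diary data go into the eCRF, but the protocol does not say in what form a reaction not judged an AE is held there.

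**The case against.** The strongest reply is that the two texts can be read together. Section 8.3.7.2 defines an ISR as an AE at the injection site, so its reporting sentence could apply only to events already judged to be AEs. The footnote would then describe the ordinary step between a diary entry and an AE record, with 10.4.1 as the criterion. This softens the conflict but does not remove it. The footnote decides the AE status of events it has already named as injection site reactions, and Table 3 and Section 6.4 treat such reactions as AEs without any further step.

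It is fair to add that the protocol is not without a criterion. The general definition exists and is tied to investigator recording; the gap is in the footnotes and for local reactions specifically.

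There are also safeguards: diary review at every on-site visit, source data verification, site training and routine monitoring. Table 3 describes most AEs in earlier experience as mild, short-lived site reactions, so mild ones were being recorded as AEs in those studies. These points weigh against large omissions. They do not say which rule sites in this study followed.

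**Conclusion.** The inconsistency is real and should be reconciled. Relative to 8.3.7.2, following the footnote can only lower the ISR count or leave it unchanged. The size cannot be derived from the documents and could be zero. The CRF completion guidelines named in Section 10.1.7, which are not among the documents, may have settled the rule for all sites.

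A reader might infer more, and the documents do not support it:

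- *That ISRs were undercounted or that sites differed.* Nothing shows that any reaction was omitted.
- *That reactions seen on-site are also discretionary.* The words about all reported reactions allow this reading, but the footnote opens with the off-site case.
- *That the share of home doses bounds the effect.* It does not. A reaction noticed after leaving the site following an on-site dose also goes in the diary, and Section 10.6.3.3 lets a home nurse perform mandatory site visits during the pandemic, so on-site dosing was not absolute.
- *That the primary AE incidence is unreliable.* The proportion with any AE moves only for participants with no other AE.

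**What to change.** **Final analysis.** The SAP is dated 31 January 2025, after the protocol's participation limit of 31 December 2024, so the collection rule can no longer be changed for this study. Leave the schedule copy in SAP 9.4.2 as it is, because editing it alone would create a new mismatch with the protocol. State in the SAP or the CSR which reporting rule sites applied, citing the CRF completion guidelines if they settle it. If the eCRF holds diary-recorded site reactions that were not entered as AEs, show them in one supportive listing or table. If it does not, give possible under-ascertainment as a limitation of the ISR incidence.

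**If the protocol is amended or reused.** Change Table 1 footnote x, Table 2 footnote q and the SAP copy together so that they match 8.3.7.2. Suggested wording: each injection-site reaction recorded in the diary or seen on-site is entered as an AE; the investigator confirms that the entry is a site reaction and assesses its severity and relatedness. This keeps a check on misdirected or duplicate entries without leaving AE status open.

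**Cost.** One sentence and at most one extra display, with no amendment needed for the final analysis. The downside is that extra display and a less favourable caveat on the ISR incidence.
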